Apparatus. The perimetry apparatus (similar to that used for animals, scaled for humans) consists of a ~2m diameter semicircular arena with independently-controlled LEDs (space 2.5°) and speakers (spaced 10°) subtending the central 180° of space embedded in the arena wall. Subjects are seated with their chins in a rest while their eyes are tracked by a high-speed camera (ISCAN ETL200). They acquire fixation of a central spot to initiate a trial (but are not forced to maintain fixation during stimulation). They then make saccades to visual or auditory targets as they appear. Latency of movement and final eye position are recorded. All training, and the training/testing of low-level tasks, takes place in this apparatus. A complementary virtual reality (VR) apparatus provides a platform for training and for testing both low-level and high-level vision, and consists of an HTC Vive Eye Pro with eye-tracking capabilities. Custom software developed in C++ and the Unreal Framework presents visual and auditory stimuli within an immersive 3-D environment. Manual HTC controllers are used to control a set of virtual hands to “point” to targets, with latency and final position of eye, gaze, and hand all tracked and recorded. A microphone records subject verbal responses of confidence in both apparatuses. The VR apparatus provides great flexibility in the delivery of training and testing stimuli, and may be used in either setting.

Multisensory training: Multisensory training is accomplished in the perimetry apparatus under dark (.001 lux) and quiet (~30 dB) ambient conditions. Each session begins with 10 mins of briefing and

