Visual tests: Tests of vision will be conducted on both sides of space and are organized in trials. In each trial the subject acquires fixation for 500 ms before a stimulus is presented after a randomized delay (200-600 ms). Subjects are required to saccade or point to (i.e., “indicate”) the stimulus or stimulus-target (<10° error) within 2 seconds or their response is scored as a “No-Go”. They are informed of whether their response was “correct” or “incorrect” via an auditory tone after a confidence report (see below). Each test has one or more stimulus levels that are manipulated to create the independent variable(s) of psychometric functions of performance. Detection/Localization: Trials contain either a visual target (LED or 5X5° white square) of manipulated contrast at a randomly-selected location outside of central space (correct response: indicate), or no stimulus anywhere (correct response: No-Go). Competition: Trials contain either no stimuli (correct response: No-Go), or 1 stimulus at a randomly-selected location on either side of space (correct response: indicate), or 2 identical visual stimuli at homotopic locations with randomized eccentricity (correct response: indicate both). Stimulus contrast is manipulated. Multisensory Integration: Trials contain either no stimuli (correct response: No-Go) or brief (100 ms) low-contrast visual or low-volume auditory stimuli presented alone or together at a randomly-selected location (correct response: “indicate”). This evaluates whether the senses can be used synergistically in contralesional space to enhance localization as in intact subjects. Frequency Discrimination: Pairs of oriented gratings with manipulated Δ° and Δf presented on either side of space (correct response: indicate if same, No-Go if different). Shape Discrimination: Unilaterally-presented pairs of simple Efron shapes (see (Whitwell et al., 2014)) with manipulated similarity (correct response: indicate if same, No-Go if different). These shapes consist of stacked rectangles or smoothed splines whose similarity can be quantitatively manipulated and provide a robust, common, and controlled way of assessing shape perception in normal and compromised populations. Subjects will also have the opportunity to report qualitative aspects of any changes in their visual perception during the study.

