Testing conditions: Each of the above tests will be evaluated under two different ambient light conditions: normal indoor levels (~300 lux) and darkness (~.001 lux). Lighting conditions are set during the “briefing” period and changed during the “break” (see below), which gives time for dark- or light-accommodation. We will also evaluate conditions in which stimuli are either stationary or moving.

Confidence reports: Subject performance is tracked online and summarized in a numeric “game score” displayed to them after each testing run (see below). On each trial, after making their response (either indicating or No-Go), subjects verbally report a confidence score of 1-3 indicating their confidence in whether they are guessing (1), are unsure (2), or are very confident (3) in their response. The confidence rating translates to the points wagered for that trial. Correct responses increase the game score by double the wagered amount, while incorrect responses decrease the score by the wagered amount.

Testing structure: A 2 hr testing session is divided into two 45-min sets separated by a 10 min “break”, with a 10 min “briefing” period at the beginning and 10 min “recapitulation” period at the end.

Training/testing sessions contain only a single set. Each trial requires <3-5 seconds. Trials of a single task, stimulus level, and testing condition are conceptually organized into “runs” of 10-12 trials (~.75-1 min/run with warmup/cooldown). Two runs with the same task and testing condition, but 1-4 stimulus levels, are intermixed within a “block” of 20-96 trials (2-8 min/block). This structure provides ample time to test two blocks of each visual test (e.g., one block stationary, the other moving) within each set. However, testing will be customized for each subject in this pilot to focus on performance limits; e.g., by reducing testing of basic capabilities in later sessions, not extensively testing multiple levels of higher-order capabilities when lower-level ones are not yet intact, and initially testing with wider ranges of stimulus levels before proceeding to narrower ranges.

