Analytical Plan. The Humphrey visual field test, kinetic visual field test, and low-vision visual functioning questionnaire (LV-VFQ-48) are standard clinical tests of vision administered before and after training. We expect increases in the number of detected locations and decreases in the thresholds of detection (when detected) at each test location in the hemianopic field, for at least Goldmann size V stimuli and smaller, and significant improvements in quality of life. In addition to these common clinical assays, a more detailed picture of low- and high-level vision will be obtained from the tests described above, which produce psychometric functions (curves relating % correct responses to stimulus level) for each subject and location or side of space. Parameters of these functions describing thresholds and maximum accuracy will, alongside confidence scores and latency, be evaluated for changes over time and across subjects and sides of space in a multilevel multivariate regression model (Gelman and Hill, 2007). Maximum likelihood estimation will be used to estimate parameter distributions to guide future studies.

Human Subjects Protection

Subject Recruitment Methods. Patients will be recruited from the local subject population hospitalized/seen by Neurology at Atrium Health / Wake Forest School of Medicine. To maximize the potential for success, adults (<85) of either sex will be selected based on: (1) diagnosis of a stable homonymous hemianopia (>4 weeks) with absence of hemineglect, (2) a lesion encompassing at least primary visual cortex but sparing parietal cortex, (3) normal auditory and cognitive function, (4) willingness to participate in the three month program, (5) ability to perform the visual discriminations in their intact field. Subjects not meeting these criteria are either poor candidates for rehabilitation given the extent of the deficit relative to the known circuits responsible for recovery in animals (crit. 1-2), will not be suitable for the visual-auditory training paradigm (crit. 3-4), or have visual capabilities that cannot be adequately tested (crit. 5). Multiple (n=6) subjects will be recruited for left- and right-sided lesions. Because this is a pilot program, variance across other demographics (e.g., age, gender, race, stroke type) will be noted but are unlikely to be able to be statistically evaluated.

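### Side-level functions can mix spared with blind field because the baseline field maps are not used to classify battery targets, and LED-level functions have too few trials to fit

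*Combined protocol and SAP*

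**What the plan says.** All references are to the combined protocol and SAP.

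- **Visual tests.** Detection/Localization targets are "of manipulated contrast at a randomly-selected location outside of central space (correct response: indicate". A single competition target is "1 stimulus at a randomly-selected location on either side of space (correct response: indicate". Multisensory Integration targets are also placed at random. No candidate set, strata or weights are given. Frequency and Shape Discrimination are described only by side.
- **Apparatus.** The arena has "independently-controlled LEDs (space 2.5°) and speakers (spaced 10°) subtending the central 180° of space".
- **Testing structure.** A run is "of 10-12 trials (~.75-1 min/run with warmup/cooldown". Two runs share a task and condition, "but 1-4 stimulus levels, are intermixed within a “block” of 20-96 trials (2-8 min/block".
- **Analytical Plan.** Functions are produced "for each subject and location or side of space". Their parameters are then modelled over time and across subjects and sides. No term for location or for baseline field status is named.
- **Subjects selection criteria.** Entry needs a stable homonymous hemianopia and a lesion including at least primary visual cortex. Complete field loss is not required, and sparing is not limited.
- **Design.** The task battery, a kinetic field and a 30-2 field are obtained before training, and both fields are repeated at the end. Nothing links the maps to the battery's target locations.
- **Design and Outcome Measure(s).** The main hypotheses are all-or-none (a task can be done to some degree or cannot be done), and any regained visual function counts as success. No numerical criterion relative to baseline is given.

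**The concern.** The study has to show that responses come from field that was blind before training. The two units of analysis offered, location and side, each have a difficulty.

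By location, the trials may be spread too thinly to support a threshold or a maximum accuracy. By side, the unit is the whole hemifield. If part of it was seen at baseline, the affected-side function averages seen and blind positions. Two things follow. A real gain in the blind part shows up smaller than it is. And because the main hypotheses are all-or-none, a few chance hits in a spared strip could be read as a new ability if none happened to occur at baseline. With six participants and no numerical success rule, one such reading would carry weight in the proof of concept.

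**Working it through.** **1. Reproduce the block size.** 2 runs × 10 to 12 trials × 1 to 4 levels = 20 to 96 trials, which matches Testing structure. One level therefore gets 2 × 10 to 2 × 12 = 20 to 24 trials per block, over both sides and including any no-stimulus trials.

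**2. Trials per location.** LED positions: 180/2.5 + 1 = 73, or 72 without the centre. The extent of central space and the share of no-stimulus trials are not stated, so a range is shown. Trials per level per location = trials per level × (1 − no-stimulus share) / number of locations.

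| Locations | No no-stimulus trials | Half no-stimulus trials |
|---|---|---|
| 72 LEDs, one block | 0.28–0.33 | 0.14–0.17 |
| 18 bins of 10°, one block | 1.1–1.3 | 0.6–0.7 |
| 4 zones, one block | 5–6 | 2.5–3 |
| 72 LEDs, four blocks | 1.1–1.3 | 0.6–0.7 |
| 4 zones, four blocks | 20–24 | 10–12 |

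Leaving out ±10° instead gives 73 − 9 = 64 positions and at most 24/64 = 0.38. Four blocks means two blocks in each of two sets, and it merges lighting and motion conditions. These are upper figures: five tests × two blocks × 2–8 min = 20–80 min against a 45-min set, so the largest blocks cannot all fit. LED-level functions are out of reach within a session. A few coarse zones are feasible.

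**3. By side, with no recovery.** Let f be the spared share of affected-side positions. The documents give no value, so f = 5%, 10% and 20% are assumptions. Assume also 95% hits in the spared part, none in the blind part, and independent trials. The pooled hit rate is p = 0.95f at baseline and later, so the expected change is zero. One level in a full block gives at most 24/2 = 12 affected-side trials.

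P(0/12 at baseline, then at least 1/12 at one later test) = (1 − p)^12 × [1 − (1 − p)^12].

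| f | p | P(0/12) | P(at least 1/12) | Product |
|---|---|---|---|---|
| 5% | 0.0475 | 0.558 | 0.442 | 25% |
| 10% | 0.095 | 0.302 | 0.698 | 21% |
| 20% | 0.19 | 0.080 | 0.920 | 7% |

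Sensitivity, in the same order of f:
- 6 trials per test (half no-stimulus): 19%, 25%, 20%.
- 10 trials: 24%, 23%, 11%.
- 24 trials: 21%, 8%, 0.6%.
- 12 trials at baseline and at any of six later tests (the six is an assumption): 54%, 30%, 8%.

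**4. Dilution.** If the blind part goes from 0 to hit rate r, the side-level change is (1 − f)r, so 20% spared shrinks it to 80% of its true size. Recovery confined near the trained position is averaged down much further. With (90 − 10)/2.5 = 32 positions per side beyond 10°, full recovery at 45° ± 5° (5 positions) raises side-level accuracy by at most 5/32 = 16 points.

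**The case against.** The strongest reply is that the plan has a baseline. The same battery is run before training, and the Analytical Plan evaluates change over time. Sparing that is present throughout has zero expected change, so a baseline-adjusted comparison is not biased by it. This stands. A reader might infer that a spared area would generally pass as rehabilitated vision, or might quote the 44%, 70% or 92% chance of at least one hit in 12 trials as a false-recovery rate. The documents support neither. Those figures apply equally at baseline, and a false change from none to some needs zero baseline hits. In 40 trials that has probability 14%, 1.8% or 0.02% for the three spared shares, so larger spared areas and more trials make this error rarer.

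A reader might also infer that random placement makes location functions impossible. It does not. The custom software places the targets, so their positions can be recorded, and coarse zones are workable. The obstacle is trials per location. Scoring accepts errors of up to 10°, so 2.5° was never a natural analysis unit.

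Finally, location-specific evidence exists. Training sessions include single visual stimuli at a fixed 45° on either side, and the clinical fields are read at each test location. This also stands, but it does not cover the battery. The 45° probes use one fixed intensity and so yield a detection rate, not a function. The clinical fields do not measure discrimination, competition, confidence or latency. No text says that the all-or-none reading is adjusted for baseline.

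**Conclusion.** The concern holds in a limited form. The unit of analysis is left open between location, which at LED resolution gets about a third of a trial per level per block, and side, which can mix spared and blind field. The baseline maps that could separate the two are collected but not used for the battery. The consequences are dilution of true recovery and, at about 12 affected-side trials per level, a 7% to 25% chance per participant and level that stable sparing looks like a change from no hits to some at one later test.

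That range rests on assumed spared shares of 5% to 20%, 95% hits in spared field, none in blind field, and a reading in which a single hit counts. The plan states no one-hit rule; it states no numerical rule at all. With complete field loss the side-level mixing disappears. The trial-count limit at LED resolution does not depend on sparing, and it applies to the perimetry arena, since no position grid is given for the virtual-reality apparatus.

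**What to change.** Change the Analytical Plan and leave the stimuli as they are. Random presentation shows how far recovery spreads from 45° and keeps targets unpredictable under trial-by-trial feedback, so replacing it with a few fixed positions would be a trade-off, not a clear gain.

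- Record the location of every target.
- Before training, classify locations as seen or blind from the baseline kinetic and 30-2 fields (the kinetic field beyond 30°) and the baseline battery. Where battery trials help to classify, use different baseline runs as the comparator; otherwise regression to the mean is built in.
- Define a few coarse zones. Fit affected-side functions only in baseline-blind zones, and judge recovery there as change from baseline.
- Report baseline-seen zones separately. Report the trained 45° zone separately too, alongside the 45° probes from the training sessions.
- Drop fitted thresholds at LED level.

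The cost is a few sentences and a location field in the data set. The fields are already collected, so no visit or test is added. The downside is small: fewer trials enter the main affected-side fit, and some boundary locations will be classified imprecisely, more so where an earlier 30-2 on file replaces a new one.

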Outcome Measure(s). A variety of dependent measures are extracted during these experiments, including responses selected, response delay/timing, response accuracy, etc. Responses to visual stimuli will be evaluated over the duration of the experiment to assess recovery of function. The main hypotheses state that subjects will either be able to perform some task at some level or not at all, although there is likely to be quantitative variation in parameters such as response latency, threshold sensitivity, and confidence. In this context, recovery of any visual function is a success. Below we outline two sets of predictions identifying the most credible outcomes and elaborate on the significance of each, although mixed results are also possible.

Modest Rehabilitation: It is possible that hemianopic patients will recover basic reflexive visual functionality, but their capabilities will be limited to those typically associated with “blindsight”. In this case, they would be able to detect and localize visual stimuli in the rehabilitated field and use auditory information to enhance this capability. However, they would always choose the intact field in competition tasks, be unable to perform any higher-order discriminations in the contralesional field, and would always

have low confidence in that field even when they can perform visually – a result falling short of that seen in the animal model. Such a result will be less than expected but is not without clinical value: by acquiring the ability to respond to contralesional visual stimuli, rehabilitated subjects can bring them into the sighted field for further analysis.

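### Competition test: because pairs are mirror images and scoring is % correct, a participant who loses the blind-side target under competition can be scored correct by pointing to the mirror position

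*Combined protocol and SAP*

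**What the plan says.** Methods and Measures, Visual tests, defines three kinds of Competition trial:

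- No stimulus: "Competition: Trials contain either no stimuli (correct response: No-Go".
- One stimulus: "or 1 stimulus at a randomly-selected location on either side of space (correct response: indicate".
- Two stimuli: "or 2 identical visual stimuli at homotopic locations with randomized eccentricity (correct response: indicate both".

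A response counts if it indicates "the stimulus or stimulus-target (<10° error) within 2 seconds". Participants learn whether they were right "via an auditory tone after a confidence report". Under Confidence reports, the stated confidence of 1 to 3 is also the wager: "Correct responses increase the game score by double the wagered amount, while incorrect responses decrease the score by the wagered amount".

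Outcome Measure(s) uses the test to describe the Modest result. Those patients can detect and localise blind-side stimuli, but: "However, they would always choose the intact field in competition tasks". The Analytical Plan works from tests "which produce psychometric functions (curves relating % correct responses to stimulus level", fitted per subject and per location or side, with threshold and maximum accuracy as the parameters.

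The documents do not give the mix of trial types. They do not say whether a second indication on a one-stimulus trial is wrong, and they describe no correction for responding to both sides when only one stimulus was shown.

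**The concern.** Homotopic means mirror positions, so randomising eccentricity moves the pair but never separates its members. Anyone who locates the intact-side target knows where its partner would be, and entry requires that participants can do the visual tasks in the intact field. Indicating both sides on a two-stimulus trial is therefore not, by itself, evidence that the blind-side stimulus was perceived.

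The participant most affected is the one in the Modest description, who responds to a blind-side stimulus shown alone and loses it when an intact-side stimulus competes. This participant passes the single blind-side trials honestly, so those trials cannot expose mirror responding. To this participant a two-stimulus trial looks like a single intact-side trial. Responses to both sides on single intact-side trials are the only internal check, and the plan does not use them. At stake is whether Competition can separate loss under competition from genuinely competitive blind-side vision.

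**Working it through.** The documents give no chance level or guessing rate for this test, so there is no planned figure to reproduce. What follows is derived from the scoring rules.

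**Inputs from the documents:** mirror-position pairs, indicate both, error below 10°, reward of +2 × wager or −1 × wager.

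**Assumptions:** an idealised Modest participant who is correct on no-stimulus and single blind-side trials, always locates the intact target, and never perceives the blind-side target when both are shown. On any trial where the intact target is seen, the participant adds the mirror position with probability q. Trial shares are n (none), i (single intact), b (single blind) and t (two stimuli).

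**1. Two-stimulus accuracy** = q × P(|pointing error| < 10°). With normal error the second factor is 2Φ(10/SD) − 1. At q = 1:

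| Assumed pointing SD | 2.5° | 5° | 7.5° | 10° | 15° |
|---|---|---|---|---|---|
| Two-stimulus % correct | 100 | 95 | 82 | 68 | 50 |

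**2. Overall accuracy, exact pointing.** If an extra indication is wrong: n + b + i(1 − q) + tq. The change from q = 0 to q = 1 is t − i. If an extra indication is not penalised: n + b + i + tq.

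| Assumed mix | q = 0 | q = 1, extra scored wrong | q = 1, extra not penalised |
|---|---|---|---|
| None/one/two at 1/3 each, singles split by side | 1/3 + 1/6 + 1/6 = 67% | 1/3 + 1/6 + 1/3 = 83% | 100% |
| Four types at 1/4 each | 75% | 75% | 100% |
| 20/60/20, singles split by side | 20 + 30 + 30 = 80% | 20 + 30 + 20 = 70% | 100% |

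**3. Feedback and points.** When only the intact target is seen, mirroring is correct with probability p = t/(t + i): 2/3, 1/2 and 0.4 in the three mixes. Expected points are w(2p − (1 − p)) = w(3p − 1), positive when p > 1/3. At w = 3, mirroring earns 3.0, 1.5 and 0.6 points per such trial. Reporting only the seen target, correct with probability 1 − p, earns 0, 1.5 and 2.4. The first mix rewards mirroring, the second is neutral and the third discourages it. In all three, a mirror response made for points favours the top wager, so a high confidence report does not rule it out.

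**4. Occasional mirroring.** Design frames the hypotheses as performing a task at some level or not at all. With q = 0.1, the chance of at least one correct two-stimulus trial is 1 − 0.9^10 = 65% in 10 such trials and 1 − 0.9^12 = 72% in 12.

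**5. Difference score.** Let s be the true rate of perceiving the blind-side target under competition, and let m = q × P(|error| < 10°). Blind-side indications on two-stimulus trials occur at rate s + (1 − s)m, and mirror-location indications on single intact-side trials at rate m. The difference is s + (1 − s)m − m = s(1 − m). It is zero when s = 0 whatever m is, and positive when s > 0 and m < 1.

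**The case against.** A reader might infer that a fully blind participant could pass as recovered, or that Competition results carry no evidence. The documents support neither reading.

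- Design re-assesses the battery only after blind-side responsiveness appears, and Testing structure limits higher-level testing while lower-level ability is lacking. Apart from baseline, a fully blind participant should rarely reach repeated Competition testing.
- Such a participant would fail every single blind-side trial. Mirroring at q = 1, with extra indications scored wrong, gives 100% on pairs and 0% on singles on both sides, a profile hard to mistake for recovery. Detection/Localization would also stay at zero on the blind side.
- Mirroring cannot by itself produce the Expected result, which requires some performance on every task, including frequency and shape discrimination.

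The strategy is also not something learned in training. The training stimuli contain no pairs, and the correctness tones are described for the visual tests. Testing can reward mirroring, but whether it does depends on the unstated mix.

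The plan also analyses by side of space, lists the responses selected among its measures, and records final positions, so the data needed for a check will exist. All of this stands, and it limits the consequence. It does not remove the problem for the Modest participant: single blind-side trials are passed, splitting by side still counts mirror responses as blind-side hits, and no comparison with single intact-side trials is specified.

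**Conclusion.** The point holds in a limited form. Two-stimulus % correct can be inflated, to a ceiling of 100%, without any perception of the blind-side target under competition. The ceiling assumes the intact target is always seen, the mirror position is always added within the 2-second window, and pointing stays within 10°. Low contrast and pointing error reduce it.

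The effect on overall % correct depends on the mix and on how extra indications are scored. It is a gain of 16.7 percentage points, no change, or a loss of 10 points in the three assumed mixes when extras are wrong. If extras go unpenalised, mirroring always pays. Pooled % correct is therefore not a dependable safeguard.

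The consequence is confined mainly to distinguishing loss under competition from competitive blind-side vision in someone who already localises single blind-side stimuli. It does not undermine the other tests. With six participants and no control group, one misread participant would still matter, and the correction is cheap enough that it should be made.

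**What to change.** In Visual tests, state that on a single intact-side trial an additional indication on the blind side is a false alarm, and state the mix of trial types. In the Analytical Plan, judge Competition recovery at each contrast by the rate of blind-side indications on two-stimulus trials minus the rate of mirror-location indications (same 10° tolerance) on single intact-side trials. Use this in place of two-stimulus % correct, and report both rates beside the difference.

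The cost is a little more analysis and a noisier score, with no new trials. With equal rates and equal trial numbers the standard error rises by √2 = 1.41; when false alarms are rare it hardly rises. The difference also understates true perception by the factor 1 − m, so it is uninformative for a participant who mirrors every time. Showing both rates makes that visible.

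Unequal eccentricities within pairs are not recommended as a remedy, because the two competitors would then differ in more than side.

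The difference score addresses inference from position only. Apparatus does not enforce fixation during stimulation, so an eye movement that brings the second stimulus into the intact field remains a separate route to a correct response.

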The Expected Result: However, our expectation is that hemianopic patients will recover visual functionality similar to that observed in the animal model, although the timing of the recovery and the quantitative parameters of the functional endpoints may differ. This means that, after a few weeks of training, they will be able to perform each of the tasks at some level under some conditions. We expect performance to be best under scotopic conditions and for moving stimuli; i.e., testing conditions best suited to driving robust visual responses in SC-mediated visual pathways. There is likely to be an initial separation between performance in visual tasks and confidence, with the former recovering faster than the latter, as the brain adapts and reinterprets activity patterns in remaining circuits as definitive of the visual stimuli generating them.

In either case, future directions will examine the means to improve the rehabilitation method (including calibrating subjects to the sensation of contralesional visual stimuli), examining the impact of the strategy on other domains impacting quality of life (e.g., navigation), an analysis of the underlying circuits using magnetoencephalography, evaluation of the sensitivity of different individual features to the procedure (e.g., age, gender, delay from lesion onset to treatment), a deeper exploration of the limits of functional recovery, and the formalization of a clinical trials protocol.

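### On two-stimulus Competition trials, percent correct shows only how often both targets were indicated, so on its own it cannot fully test the predicted choice of side

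*Combined protocol and SAP*

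**What the plan says.** Three parts of the combined protocol and SAP bear on the Competition test.

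- **Visual tests (Methods and Measures).** Besides empty trials, Competition has trials with "1 stimulus at a randomly-selected location on either side of space (correct response: indicate" and trials with "2 identical visual stimuli at homotopic locations with randomized eccentricity (correct response: indicate both". A two-stimulus trial therefore gets one right/wrong score, and it is right only when both targets are indicated.
- **Outcome Measure(s).** Under Modest Rehabilitation, participants recover detection and localization, but "they would always choose the intact field in competition tasks". Under The Expected Result, "they will be able to perform each of the tasks at some level under some conditions". The same section lists what is collected: "A variety of dependent measures are extracted during these experiments, including responses selected, response delay/timing, response accuracy, etc".
- **Analytical Plan.** The tests yield psychometric functions, described as "curves relating % correct responses to stimulus level) for each subject and location or side of space". The model is then specified: "Parameters of these functions describing thresholds and maximum accuracy will, alongside confidence scores and latency, be evaluated for changes over time". No choice or side-preference variable is named, and no rule says how a trial with a target on each side enters a by-side curve.

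**The concern.** The scoring rule, the prediction and the analysis do not line up. The Modest Rehabilitation prediction concerns which of two targets is chosen. The score records only whether both were indicated, so indicating the intact target alone, the blind-side target alone, or neither all count as the same error. The analysis then splits percent correct by location or side, although a bilateral trial has one score and two sides.

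What is at stake is the reading of partial competitive recovery. Suppose a participant's blind-side target sometimes wins but both are rarely reported. That participant would look, on two-stimulus percent correct, like one whose blind-side target never wins. The background section cites competitive visual processing as part of the recovery in the animal model, and Outcome Measure(s) uses Competition as one marker of whether recovery falls short of it.

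**Working it through.** The plan states no accuracy figure, trial mix, power or error rate for Competition, so there is no figure to reproduce. The check follows the scoring rule through the possible responses.

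**Step 1: define the outcomes.** Each two-stimulus trial ends in one of four ways, with probabilities summing to 1: intact only (I), blind side only (B), both (D), neither (N). Then:

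- percent correct under the plan's rule = D
- blind-side target indicated = B + D
- intact-side target indicated = I + D

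**Step 2: put in response patterns.** These are illustrative assumptions.

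| Pattern | I | B | D | N | Percent correct | Intact indicated | Blind side indicated |
|---|---|---|---|---|---|---|---|
| Always intact (the Modest prediction) | 1 | 0 | 0 | 0 | 0% | 1.0 | 0.0 |
| Always blind side | 0 | 1 | 0 | 0 | 0% | 0.0 | 1.0 |
| One side at random | 0.5 | 0.5 | 0 | 0 | 0% | 0.5 | 0.5 |
| No response | 0 | 0 | 0 | 1 | 0% | 0.0 | 0.0 |
| Both 40%, rest intact | 0.6 | 0 | 0.4 | 0 | 40% | 1.0 | 0.4 |
| Both 40%, rest split | 0.3 | 0.3 | 0.4 | 0 | 40% | 0.7 | 0.7 |
| Both 40%, rest blind side | 0 | 0.6 | 0.4 | 0 | 40% | 0.4 | 1.0 |
| Always both | 0 | 0 | 1 | 0 | 100% | 1.0 | 1.0 |

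For a given percent correct D, the blind-side rate B + D can lie anywhere from D to 1. At 0% the score leaves it wholly undetermined. At 40% it leaves a range of 60 points. This does not depend on the mix of trial types.

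**Step 3: what percent correct can show.** Always choosing the intact target implies D = 0, so a genuine D above 0 contradicts it. Run sizes are 10 to 12 trials (Testing structure). Assume a whole run consisted of independent two-stimulus trials. If none is correct, the one-sided 95% upper bound for D is 1 − 0.05^(1/n): 25.9% for n = 10 and 22.1% for n = 12. If D is truly 20%, the chance of at least one correct trial is 1 − 0.8^n: 0.893 and 0.931. The plan does not give the split between trial types. Fewer two-stimulus trials per run would weaken these figures.

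**Step 4: pooling.** Suppose empty, one-stimulus and two-stimulus trials were pooled in equal thirds, with every empty and one-stimulus trial correct. Always-intact responding gives 1/3 + 1/3 + 0 = 67%. Choosing one side at random also gives 67%, despite a 50-point difference in blind-side choice. Always indicating both gives 100%. With mixes of 0.2/0.4/0.4 and 0.25/0.5/0.25 the tied value is 60% and 75%. The plan does not say that trial types are pooled, so this only illustrates Step 2.

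**Step 5: assignment to a side.** A one-stimulus trial has a side. A two-stimulus trial has a target on each side and one score, so placing that score in either side's curve would be arbitrary.

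**The case against.** A reader might infer that the Competition test cannot distinguish blindsight-like recovery from competitive recovery at all. The documents do not support that, for four reasons.

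- The Expected Result is that each task can be done at some level. For two-stimulus trials this means D above 0, which percent correct does measure and which excludes exclusive intact-field choice. Between always intact and always both, the score differs by 100 points.
- One-stimulus Competition trials can be analysed by side as planned.
- The chosen responses are already listed as an extracted measure, separately from accuracy. The gap is in the defined analysis, not in a failure to collect data.
- The exact tie in Step 4 needs a participant who chooses the blind-side target half the time yet never indicates both. Each such response would draw an incorrect tone and lose wagered points. That pattern is possible, but the plan does not predict it.

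It is also fair to say that this is a six-person pilot with qualitative hypotheses, that Competition is one of five tests, and that the plan counts recovery of any visual function as a success and allows for mixed results.

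All of this stands and limits the point. It does not remove it. Extracting the responses does not put them into the analysis, and the Analytical Plan names only thresholds, maximum accuracy, confidence and latency. A can-or-cannot hypothesis also makes the definition of success matter more: a participant who reliably indicates only the blind-side target would be classed as unable on two-stimulus trials.

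**Conclusion.** The point holds in a limited form. Two-stimulus percent correct equals the probability of indicating both targets. Above 0, if genuine, it refutes exclusive intact-field choice. At 0% it does not separate four quite different response patterns, and at any intermediate value it does not show which side was chosen on the remaining trials. Percent correct alone therefore cannot test the side-choice prediction in full, and a bilateral trial's single score does not belong in a by-side curve.

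The equality and the range from D to 1 follow from the scoring rule alone. The 40% patterns, the run-sized bounds and the pooled percentages rest on the assumptions stated with them. No sample size or error rate depends on this point. It affects how one of the plan's markers of recovery is interpreted, and it should be settled before testing starts.

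**What to change.** In the Analytical Plan:

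1. Classify each two-stimulus trial as intact only, blind side only, both or neither, using the responses already extracted. Confirm that the record shows every target indicated, since the Apparatus paragraph lists only movement latency and final eye position for the perimetry setup.
2. For the side-choice prediction, report the proportion of two-stimulus trials with the blind-side target indicated (B + D). Set it against the same participant's blind-side rate on one-stimulus Competition trials. Without that comparison, a low value could reflect a target that is not seen even when shown alone.
3. Report the both-indicated rate beside it. The existing rule for a correct response can stay and need not become secondary.
4. Keep two-stimulus trials out of the by-side percent-correct curves.

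Recording which target was indicated first is optional. The cost is slightly more scoring and analysis work, with no added participants, sessions or trials.
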